4.2.7. Prior and Concomitant Therapy

Therapy prior to enrollment with any other experimental treatment or off-label use of marketed medications that are intended as specific treatment for COVID-10 or the SARS-CoV-2 infection (i.e., post-exposure prophylaxis) are permitted but must be discontinued on enrollment. There is no waiting period between discontinuation of these treatments and infusion of study product. However, these prior treatments and their end date should be documented on the Concomitant Medication form.

If the local standard of care per written policies or guidelines for treatment for COVID-19 or SARS-CoV-2 infection (i.e., not just an individual clinician decision) includes lopinavir/ritonavir (Kaletra), hydroxychloroquine or other agents (e.g. those targeting the host immune response), then continuing these during the study is permitted, but may require additional safety monitoring as determined by the treatment clinician. Additionally, there should be plans on how the concomitant drugs are stopped for additive toxicities (Protocol Section 6.1.4). If there are NO written policies or guidelines for local standard of care, concomitant use of any other experimental treatment or off-label use of marketed medications intended as specific treatment for COVID-10 or SARS-CoV-2 infection are prohibited. This includes medications that target the host immune response.

There is no available data on potential interactions between remdesivir and other anti-SARS-CoV investigational agents. Administering remdesivir concurrently with other agents may lead to antagonism or synergy or may have no effect.

Concomitant medications will be assessed only from 7 days prior to enrollment to Day 11 or upon discharge, whichever comes first.

Of note, acetaminophen is prohibited during the study through Day 15, even if clinically indicated for a subject.

4.2.8. Treatment Compliance

All subjects should receive a loading dose and up to 9 maintenance doses while hospitalized. If a subject is no longer hospitalized, then infusions will no longer be given. Any dose that is missed is not made up; the total course should not exceed 10 calendar days even if an infusion is missed. If the eGFR decreases to an eGFR < 25 ml/min, the study infusion should not be given on that day. The infusion may be resumed on the next day if the eGFR returns to ≥ 30 ml/min. If the subject's renal function worsens to the point that they require hemodialysis or hemofiltration, study product will be discontinued. If the ALT and/or AST increases to > 5 times upper limits of normal, the dose of remdesivir should be held and not be restarted until the ALT and AST ≤ 5 times upper limits of normal.

All doses will be recorded on the appropriate eCRF. Total volume and whether the IV was slowed or halted will be recorded to track compliance.

4.3. Efficacy and Safety Variables

For each study day while the patient is hospitalized, the clinical status will be recorded on an 8-point ordinal scale as follows:

- Day 1 – The clinical assessment at the time of randomization.
- Day 2 - The most severe assessment occurring at any time between randomization and midnight the day of randomization.
- Day 3+ - The most severe assessment occurring from midnight to midnight (00:00 to 23:59) of the prior day (e.g., the value recorded on Day 3 will be the most severe outcome that occurred on Day 2).

where the clinical status scale is defined as follows:

8. Death;
7. Hospitalized, on invasive mechanical ventilation or ECMO;
6. Hospitalized, on non-invasive ventilation or high flow oxygen devices;
5. Hospitalized, requiring supplemental oxygen;
4. Hospitalized, not requiring supplemental oxygen- requiring ongoing medical care (COVID-19 related or otherwise);
3. Hospitalized, not requiring supplemental oxygen - no longer requires ongoing medical care;

2. Not hospitalized, limitation on activities;
1. Not hospitalized, no limitations on activities

A modified version of the ordinal scale will be used in sensitivity analyses of the primary and secondary outcomes. The modified scale will be as follows:

8. Death;
7. Hospitalized, on invasive mechanical ventilation or ECMO;
6. Hospitalized, on non-invasive ventilation or high flow oxygen devices;
5. Hospitalized, requiring supplemental oxygen;
4. Hospitalized, not requiring supplemental oxygen- requiring ongoing medical care (COVID-19 related or otherwise);
3. Not hospitalized, limitation on activities;
2. Hospitalized, not requiring supplemental oxygen - no longer requires ongoing medical care; or Not hospitalized, no limitations on activities.

That is, category 1 and 3 of the original scale will be combined into the lowest category.

NEWS has demonstrated an ability to discriminate subjects at risk of poor outcomes. This score is based on 7 clinical parameters (see [Table 1](#)). This should be evaluated at the first assessment of a given study day and prior to administration of study product. The 7 parameters can be obtained from the hospital chart using the last measurement prior to the time of assessment and a numeric score given for each parameter (e.g., a RR of 9 is one point, oxygen saturation of 92 is two points). This is recorded for the day obtained. i.e., on Day N, the Day N score is obtained and recorded as the Day N score.

Table 1: Categories of the NEWS scale.

PHYSIOLOGICAL PARAMETERS	3	2	1	0	1	2	3
Respiration Rate	≤8		9 - 11	12 - 20		21 - 24	≥25
Oxygen Saturations	≤91	92 - 93	94 - 95	≥96			
Any Supplemental Oxygen		Yes		No			
Temperature	≤35.0		35.1 - 36.0	36.1 - 38.0	38.1 - 39.0	≥39.1	
Systolic BP	≤90	91 - 100	101 - 110	111 - 219			≥220
Heart Rate	≤40		41 - 50	51 - 90	91 - 110	111 - 130	≥131
Level of Consciousness				A			V, P, or U

Oxygenation, Non-invasive ventilation/high flow oxygen, Invasive Mechanical Ventilation / extracorporeal membrane oxygenation (ECMO), hospitalization and mortality will be assessed using results of the 8-point ordinal scale and post discharge eCRF questions.

Safety will be assessed by the following:

- Cumulative incidence of serious adverse events (SAEs) through 28 days of follow-up.
- Cumulative incidence of Grade 3 and 4 AEs.
- Discontinuation or temporary suspension of infusions (for any reason)
- Changes in white cell count, absolute neutrophil count, hemoglobin, platelets, creatinine, glucose, total bilirubin, ALT, AST, and PT over time.

Clinical labs will be drawn on Days 1, 3, 5, 8, 11 and on Day 15 and 29 if the subject is able to return to the clinic or is still hospitalized.

Virologic efficacy is an exploratory endpoint and will be assessed by the following:

- Qualitative and quantitative PCR for SARS-CoV-2 in OP swab on Days 1; 3, 5, 8, 11 (while hospitalized); and Day 15 and 29 (if able to return to clinic or still hospitalized).
- Qualitative and quantitative PCR for SARS-CoV-2 in blood on Days 1; 3, 5, 8, 11 (while hospitalized).

The schedule of study procedures is provided in [Table 2](#) below.

Table 2: Schedule of Study Procedures (from protocol version 3.0)

Day +/- Window	Screen	Baseline	Study Intervention Period	Follow-up Visits			
	-1 or 1	1	Daily until hospital discharge	15 ⁷ ± 2	22 ⁷ ± 3	29 ⁷ ± 3	
ELIGIBILITY							
Informed consent	X						
Demographics & Medical History	X						
Targeted physical exam	X						
Review SARS-CoV-2 results	X						
STUDY INTERVENTION							
Randomization		X					
Administration of remdesivir or control		Daily until discharge or 10 days. No study product given after Day 10.					
STUDY PROCEDURES							
Vital signs including SpO ₂		X ⁴	Daily until discharge	X ⁷	X ⁷	X ⁷	
Clinical data collection ¹		X ⁴	Daily until discharge	X ⁷	X ⁷	X ⁷	
Adverse event evaluation		X ⁴	Daily until discharge	X ⁷	X ⁷	X ⁷	
Concomitant medication review		X ⁴	From Day -7 to Day 11				
SAFETY LABORATORY							
Safety hematology, chemistry and liver tests	X ^{2,3}	X ^{4,5,6}	Day 3, 5, 8, 11 (all ± 1 day) if hospitalized ^{5,6}	X ⁷		X ⁷	
Pregnancy test for females of childbearing potential	X ^{2,3}						
RESEARCH LABORATORY							
Blood for plasma to test for PCR SARS-CoV-2		X ⁵	Day 3, 5, 8, 11 (all ± 1 day) if hospitalized				
Oropharyngeal swab ⁸		X ⁵	Day 3, 5, 8, 11 (all ± 1 day) if hospitalized	X ⁷		X ⁷	
Blood for serum (for secondary research)		X ⁵	Day 3, 5, 8, 11 (all ± 1 day) if hospitalized	X ⁷		X ⁷	
Notes:							
¹ Refer to Section 8.1 of the protocol for details of clinical data to be collected including ordinal score, NEWS, oxygen requirement, mechanical ventilator requirement, etc.							
² Screening laboratory tests include: ALT, AST, creatinine (and calculate an estimated glomerular filtration rate (eGFR)), and pregnancy test.							
³ Laboratory tests performed in the 48 hours prior to enrollment will be accepted for determination of eligibility.							
⁴ Baseline assessments should be performed prior to randomization. Laboratory tests performed as part of routine clinical care in the 24 hours prior to first dose will be accepted for the baseline safety laboratory tests. Baseline may be the same as the screening laboratory tests.							
⁵ Safety laboratory tests include WBC with differential, hemoglobin, platelets, creatinine, glucose, total bilirubin, ALT, AST, and PT.							
⁶ Any laboratory tests performed as part of routine clinical care within the specified visit window can be used for safety laboratory testing. Window during the 10 days of dosing is ±1 day.							
⁷ In-person visits are preferred but recognizing quarantine and other factors may limit the subject's ability to return to the site for the visit. In this case, these visits may be conducted by phone							

 • If still hospitalized at Day 15 and 29 or returns to the site for an in-person visit: Clinical data, vital signs, safety laboratory tests, and research laboratory samples (OP swab and serum only) as able. • If phone call only on Days 15 and 29 and all Day 22 visits: assess adverse events, clinical status (ordinal scale), readmission to a hospital, and mortality only. 							
⁸ Oropharyngeal swabs are preferred, but if these are not obtainable, nasopharyngeal swabs may be substituted.							

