3.2. Endpoints

Primary Endpoint

Time to recovery, where recovery is defined as clinical status in states 1, 2, or 3 of the 8-point ordinal scale, censored at Day 29.

- Clinical status of a subject (8-point ordinal scale) is defined below:
 - 8. Death;
 - 7. Hospitalized, on invasive mechanical ventilation or ECMO;
 - 6. Hospitalized, on non-invasive ventilation or high flow oxygen devices;
 - 5. Hospitalized, requiring supplemental oxygen;

4. Hospitalized, not requiring supplemental oxygen - requiring ongoing medical care (COVID-19 related or otherwise);
3. Hospitalized, not requiring supplemental oxygen - no longer requiring ongoing medical care;
2. Not hospitalized, limitation on activities and/or requiring home oxygen;
1. Not hospitalized, no limitations on activities

Secondary Endpoints

The key secondary endpoint is clinical status (8-point ordinal scale) on Day 15.

The other secondary endpoints are:

- Ordinal outcome assessed daily while hospitalized and on Days 15, 22, and 29.
- NEWS assessed daily while hospitalized and on Days 15 and 29.
- Days of supplemental oxygen (if applicable).
- Days of non-invasive ventilation/high-flow oxygen (if applicable).
- Days of invasive mechanical ventilation/ECMO (if applicable).
- Days of hospitalization.
- Date and cause of death (if applicable).
- SAEs.
- Grade 3 and 4 adverse events
- WBC with differential, hemoglobin, platelets, creatinine, glucose, total bilirubin, ALT, AST, and PT on Day 1; Days 3, 5, 8, and 11 (while hospitalized); and Days 15 and 29 (if attends in-person visit or still hospitalized).

Exploratory Endpoint

- Qualitative and quantitative polymerase chain reaction PCR for SARS-CoV-2 in OP swab on Day 1; Days 3, 5, 8, and 11 (while hospitalized); and Days 15 and 29 (if attends in-person visit or still hospitalized).
- Qualitative and quantitative PCR for SARS-CoV-2 in blood on Day 1; Days 3, 5, 8, and 11 (while hospitalized).

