3.3.2. Recovery and Time to Recovery

The primary efficacy outcome measure is the time to recovery. Recovery will be defined as having a value of 1, 2, or 3 on the clinical status 8-point ordinal scale. The time to recovery will be defined as the elapsed time (in days) from randomization to the earliest day at which a subject reaches recovery. Note that since clinical status assessments are recorded as defined in Section 4.3, the day that is being assessed (not necessarily the day the response is collected) will be used to determine the timing of events. For example, a subject with a score of 5 recorded on Days 1 - 3 and a score of 3 recorded on Day 4 will have a time to recovery equal to 3 days. It is also possible that a subject has a clinical status score > 3 reported for a particular day but was subsequently discharged on the same day. For these scenarios where a subject is discharged with no reported clinical score of 1, 2, or 3 will be considered recovered at the time of discharge.

Any subjects that are lost to follow-up or terminated early prior to an observed recovery will be censored at the day of their last observed assessment. Subjects who complete follow-up but do not experience recovery will be censored at the day of their Day 29 visit. All deaths within Day 29 (and prior to recovery) will be considered censored at 28 days. Note that we do not expect many subjects to worsen after discharge.

However, we will evaluate whether any discharged subjects subsequently experience a worse clinical status and sensitivity analyses will be conducted accordingly. For these analyses, subjects who recover but are later re-admitted will not be considered a recovery but will instead be censored at 28 days. Sensitivity analyses will be performed where subjects who were crossover treated with remdesivir (per April 29, 2020 Protocol Administrative Letter) will be censored at the time of remdesivir treatment initiation. In addition, the analyses will be replicated where subjects who were unblinded, regardless of whether they received crossover treatment of remdesivir or not, will be censored at the time of unblinding.

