6.5. Missing Data

All attempts will be made to collect all data per protocol. Any data point that appears to be erroneous or inexplicable based on clinical judgment will be investigated as a possible outlier. If data points are identified as outliers, sensitivity analyses may be performed to examine the impact of including or excluding the outliers. Any substantive differences in these analyses will be reported.

For time to event outcomes, subjects who are lost to follow-up or terminate the study prior to Day 29 and prior to observing/experiencing the event will be censored at the time of their last observed assessment. Subjects who die prior to observing/experiencing the event will be censored at Day 29.

For the analysis of the key secondary outcome, subjects who are discharged but are subsequently re-admitted prior to Day 15 without a reported clinical score, their clinical score will be imputed at 7, which is the highest value for a hospitalized subject.

For the analyses of the secondary outcomes that involve clinical score (i.e. the key secondary outcome and time to improvement), if a subject is discharged from the hospital without a previously or concurrently reported clinical score of 1 or 2, then their clinical score at the time of discharge will be imputed as 2, which is the highest value for a non-hospitalized subject.

For the modified version of the ordinal score described in Section 4.3, if a subject is discharged from the hospital without a previously or concurrently reported clinical score of 2 or 3, then their clinical score at the time of discharge will be imputed as 3, which is the highest value for a non-hospitalized subject.

For the analyses of the secondary outcomes described in Section 3.3, the following imputation rules will be used for subjects who are lost to follow-up, terminate early from the study, or do not have further outcome data available after discharge for any reason:

- Days of Non-invasive ventilation/high-flow oxygen:
 - If the subject's clinical status scale is 6 at the last observed assessment, then the subject will be considered to be on non-invasive ventilation/high-flow oxygen

- through Day 29. The endpoint will be total days when assessments are available plus all imputed days following the last observed assessment.

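### The modified ordinal scale cannot change the time-to-recovery result, so it is not a sensitivity analysis of the primary outcome; its discharge imputation rule also misses some subjects

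*SAP*

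**What the plan says.** SAP 3.2 defines the primary endpoint: "Time to recovery, where recovery is defined as clinical status in states 1, 2, or 3 of the 8-point ordinal scale". SAP 3.3.2 repeats the definition and adds that a subject "discharged with no reported clinical score of 1, 2, or 3 will be considered recovered at the time of discharge".

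SAP 4.3 introduces the second scale and its use: "A modified version of the ordinal scale will be used in sensitivity analyses of the primary and secondary outcomes". It sums up the change as follows: "That is, category 1 and 3 of the original scale will be combined into the lowest category". Categories 4 to 8 are carried over, and original category 2 becomes modified category 3. No section gives a different definition of recovery for the modified scale.

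SAP 6.5 has a discharge rule for each scale. On the original scale, a subject discharged with no earlier or concurrent score of 1 or 2 is given 2. On the modified scale the rule applies "if a subject is discharged from the hospital without a previously or concurrently reported clinical score of 2 or 3", and the value given is 3.

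In the analysis sections the modified scale returns only in SAP 8.2.1, which repeats the ordinal and time-to-improvement analyses on it. Its one shell, Table 29, is time to a two-category improvement. SAP 8.1.2, which sets out the sensitivity analyses of the primary outcome, does not mention it, and neither do the time-to-recovery shells (Tables 14 to 20).

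**The concern.** A sensitivity analysis supports a result only if it could have come out differently. If every recovered state stays recovered and every other state stays unrecovered, repeating the recovery analysis on the new scale reproduces the primary result. Reporting it as a check would suggest a robustness that was never tested.

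The imputation rule raises a different question. On the original scale, the scores that switch the rule off (1 and 2) are both non-hospitalized states. On the modified scale, category 2 also holds subjects still in hospital, so the rule can be switched off by a score that says nothing about status after discharge.

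**Working it through.** The argument is a comparison of sets. No planning figure enters it. For completeness, the SAP Section 5 event formula at a recovery ratio of 1.35 gives 4 × (1.96 + 1.0364)² / (ln 1.35)² = 35.914 / 0.09006 = 398.8, or 399 recoveries against 400 stated, so the plan's own figure reproduces.

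**Mapping (SAP 4.3)**

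| Original | Modified | Recovered, original | Modified score 3 or lower |
|---|---|---|---|
| 8, 7, 6, 5, 4 | unchanged | no | no |
| 3 (in hospital, no ongoing care) | 2 | yes | yes |
| 2 (out of hospital, limited) | 3 | yes | yes |
| 1 (out of hospital, not limited) | 2 | yes | yes |

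**Time to recovery.** Modified {2, 3} maps back to original {1, 2, 3}, so the boundary between 4 and 3 does not move. A discharge with no recovered score is a recovery on the discharge day under 3.3.2. The modified-scale imputed value of 3 is also a recovered score on that same day. The stratified log-rank z in SAP 8.1.1 uses only event times, event indicators, arm and stratum. All four are the same, and so are the Cox hazard ratio and the Kaplan-Meier medians.

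As a numerical check, 50 trials of 572 subjects were simulated and scored both ways. The daily transition rates were assumed, but the identity does not depend on them. The largest difference in event time, event indicator or z was 0; in the first trial z was 3.643 on both scales. The result moved only when recovery itself was redefined as the lowest modified category alone (original {1, 3}). The mean absolute change in z was then 0.97 under the assumed rates. The documents contain no such redefinition.

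**Time to improvement.** The states that count as improved, written in original labels, for the baseline categories 4 to 7 listed in SAP 6.4:

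| Baseline | One category | Two categories |
|---|---|---|
| 4 | {1,2,3} on both scales | {1,2} original, {1,3} modified |
| 5 | {1–4} on both | {1,2,3} on both |
| 6 | {1–5} on both | {1–4} on both |
| 7 | {1–6} on both | {1–5} on both |

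One-category improvement never changes. Two-category improvement changes only from baseline 4. The Day 15 proportional odds analysis can change, because it uses the order within the recovered categories.

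**Discharge rule (SAP 6.5).** Take a subject scored original 3 in hospital, then discharged with no later score.

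- Original scale: there is no score of 1 or 2, so the rule applies and the subject is given 2, the worse of the two non-hospitalized states.
- Modified scale: the in-hospital score is already a modified 2, because that category also covers "no longer requires ongoing medical care; or Not hospitalized, no limitations on activities". The rule does not apply, and the subject is not given 3, the corresponding worse state.

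SAP 6.5 does not say what value the subject then has. If the last score is used, which is an assumption, it is 2, the best category. Time to improvement is not affected, since such a subject has already reached the lowest modified category. The Day 15 analysis can be.

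**The case against.** The strongest reply is that no planned output rests on the sentence in 4.3. SAP 8.1.2 lists the Treated population, Fine-Gray, severity interaction, subgroups, leave-one-site-out, unsustained recovery, concomitant medication and crossover analyses. None uses the modified scale, and there is no shell for it among the recovery tables. SAP Section 15 records that the text was moved into 4.3 from Section 8, which may explain the loose reference to the primary outcome. This stands, and it keeps the point minor. It does not make the sentence right: either 4.3 commits to an analysis that cannot differ from the primary, or it promises one that Section 8 omits.

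A reader might infer that the report will present this analysis as support for the primary result. Section 8 and the shells do not show that.

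A reader might also infer that the scale was meant to test whether in-hospital category 3 should count as recovery, and that this is left wholly unexamined. The documents do not state that purpose, and the scale places category 3 level with the best state. No analysis in 8.1.2 removes category 3 from the event, but related discharge-based analyses exist: time to discharge or a NEWS of 2 or less (3.3.5, 8.2.2) and days of hospitalization (3.3.9, 8.2.9). Protocol 9.4.8 also plans comparisons at each category threshold, although SAP 8.3 leaves exploratory outcomes out of the SAP.

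Finally, the printed interval need not be identical. If the trial stopped at the interim, SAP 8.1.1 bases the primary estimate and interval on stage-wise ordering, while 8.1.2 uses plain 95% intervals. That difference has nothing to do with the scale.

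**Conclusion.** The point holds in limited form and is minor. As defined in 4.3, the modified scale gives no evidence on the robustness of time to recovery. The difference in events, times, log-rank z, Cox hazard ratio and Kaplan-Meier medians is exactly zero when both are computed by the same method. This rests on recovery meaning a score of 3 or lower on either scale, the only definition given. The scale is also uninformative for one-category improvement, and for two-category improvement except from baseline 4, assuming baseline categories 4 to 7. It is informative for Day 15 status. The primary result and the type I error rate are untouched.

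The 6.5 rule is a separate small error that bears on the modified-scale Day 15 analysis. It affects only subjects last scored original 3, then discharged without a later score. The documents give no basis for counting them, so its size is unknown.

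**What to change.** 1. In SAP 4.3, limit the modified scale to Day 15 clinical status and two-category improvement, and remove the reference to the primary outcome. Bring the repeat-analysis sentence in 8.2.1 into line.
2. In SAP 6.5, make the modified-scale imputation depend on the absence of a non-hospitalized score (original 1 or 2), as the original-scale rule does.
3. Optional, if a sensitivity analysis of the recovery definition is wanted: add to 8.1.2, with a shell beside Tables 18 to 20, time to original category 1 or 2, using the same stratified log-rank test, Cox model and death rule. SAP 2.1 says version 3.0 was written after the interim results had gone to the DSMB and been made public, so this analysis must be labelled as added after that disclosure. Its downside is that it also reflects quarantine and placement delays, which category 3 separates from medical need.

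Items 1 and 2 cost a few words each. Item 3 costs one extra table from data already collected.
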